7.5 Unscheduled Visits

If unscheduled visits occur, the Investigator must record the reason for unscheduled visit, including any AEs/ADEs that the subject or the male partner has experienced since their last visit, concomitant medication changes, withdrawal (if deemed appropriate) and any clinical assessments deemed appropriate for their clinical care.

Unscheduled visits should not alter the timing of the routine investigation schedule.

8 SAFETY REPORTING

In this investigation, safety reporting is applicable for both female subjects and male partners by following the process described in this section, which the term of 'subject' refers to both female and male partners.

Safety Reporting in the investigation are in compliance with the Regulation (EU) 2017/745, the guidance of MDCG 2020-10/1 and the guidelines on medical devices, MEDDEV 2.7/3 revision 3, May 2015.

8.1 Adverse Event Definitions

Adverse Event

An Adverse Event (AE) is any untoward medical occurrence, unintended disease or injury or any untoward clinical signs (including an abnormal laboratory finding) in subjects, users or other persons, in the context of a clinical investigation, whether or not related to the investigational medical device.

This definition includes events that are anticipated as well as unanticipated events.

This definition includes events occurring in the context of a clinical investigation related to the investigational device, the comparator or the procedures involved.

Adverse Device Effect

An Adverse Device Effect (ADE) is an AE related to the use of an investigational medical device.

This includes any adverse event resulting from insufficiencies or inadequacies in the instructions for use, the deployment, the implantation, the installation, the operation, or any malfunction of the

D8199934 V6.0, Appendix 2 – Clinical Investigation Plan

Change Control: CC220523-009

investigational medical device. This includes any event that is a result of a use error or intentional abnormal use of the investigational medical device. This includes any AE resulting from insufficient or inadequate instructions for use, deployment, implantation, installation, operation, or any malfunction of the investigational medical device. This includes any event that is a result of a use error or intentional misuse.

Device Deficiency

Any inadequacy in the identity, quality, durability, reliability, safety or performance of an investigational device, including malfunction, misuse or use errors or inadequacy in information supplied by the manufacturer.

Serious Adverse Event

A Serious Adverse Event (SAE) is any AE that led to any of the following:

- a. death,
- b. serious deterioration in health of the subject, that resulted in any of the following:
 - life-threatening illness or injury,
 - permanent impairment of a body structure or a body function,
 - hospitalisation or prolongation of patient hospitalisation,
 - medical or surgical intervention to prevent life-threatening illness or injury or permanent impairment to a body structure or a body function,
 - chronic disease,
- c. foetal distress, foetal death or a congenital physical or mental impairment or birth defect.

A planned hospitalisation for pre-existing condition, or a procedure required by the CIP, without a serious deterioration in health, is not considered to be an SAE.

This includes device deficiencies that might have led to a SAE if

- a. suitable action had not been taken or
- b. intervention had not been made or
- c. if circumstances had been less fortunate.

Serious Adverse Device Effect

A Serious Adverse Device Effect (SADE) is an ADE that has resulted in any of the consequences characteristic of a SAE.

Unanticipated Serious Adverse Device Effect

An Unanticipated Serious Adverse Device Effect (USADE) is an effect which by its nature, incidence, severity or outcome has not been identified in the current version of the risk analysis report.

Anticipated Serious Adverse Device Effect

Anticipated SADE (ASADE): an effect which by its nature, incidence, severity or outcome has been previously identified in the current version of risk analysis report.

8.2 Assessment of Adverse Events

All AEs that arise after the subject has given informed consent will be recorded in the subject's source documents and eCRF. AEs can be reported spontaneously by the subject or in response to non-leading questioning, observation by the Investigator or be a significant laboratory abnormality.

All AEs, ADEs, SAEs, SADEs and USADEs are collected, fully investigated and documented.

SAE / SADE / USADEs should be followed until resolution or stabilisation. Subjects with ongoing SAE / SADE / USADEs at investigation termination will be further followed up until recovery or until stabilisation of the disease after termination.

For each SAE, a causality assessment of the event to the investigational device, the comparator or the investigation procedure must be performed. For each AE, the relationship between the use of the investigational device (including the medical - surgical procedure) and the occurrence of each adverse event shall be assessed and categorized. The relationship must be determined by the Investigator (if medically qualified) or by a medically qualified Co-Investigator.

Relationship	Description
Not related	
Relationship to the investigational device, comparator or procedures can be excluded when:
 
 ▪ the event is not a known side effect of the product category the device belongs to or of similar devices and procedures. ▪ the event has no temporal relationship with the use of the investigational device or the procedures related to application of the investigational device. ▪ the serious adverse event does not follow a known response pattern to the investigational device (if the response pattern is previously known) and is biologically implausible. ▪ the discontinuation of investigational device application or the reduction of the level of activation / exposure - when clinically feasible - and reintroduction of its use (or increase of the level of activation / exposure), do not impact on the serious adverse event. ▪ the event involves a body-site or an organ that cannot be affected by the device or procedure. ▪ the serious adverse event can be attributed to another cause (e.g. an underlying or concurrent illness / clinical condition, an effect of another device, drug, treatment or other risk factors). ▪ the event does not depend on a false result given by the investigational device used for diagnosis, when applicable. 
In order to establish the non-relatedness, not all the criteria listed above might be met at the same time, depending on the type of device / procedures and the serious adverse event.

Possible	
The relationship with the use of the investigational device or comparator, or the relationship with procedures, is weak but cannot be ruled out completely. Alternative causes are also possible (e.g. an underlying or concurrent illness / clinical condition or / and an effect of another device, drug or treatment). Cases where relatedness cannot be assessed or no information has been obtained should also be classified as possible.

Probable	
The relationship with the use of the investigational device or comparator, or the relationship with procedures, seems relevant and / or the event cannot reasonably be explained by another cause.

Causal Relationship	
The serious adverse event is associated with the investigational device, comparator or with procedures beyond reasonable doubt when:
 
 ▪ the event is a known side effect of the product category the device belongs to or of similar devices and procedures.

- the event has a temporal relationship with investigational device use / application or procedures.
- the event involves a body-site or organ that:
 - the investigational device or procedures are applied to
 - the investigational device or procedures have an effect on
- the serious adverse event follows a known response pattern to the investigational device (if the response pattern is previously known).
- the discontinuation of investigational device application (or reduction of the level of activation / exposure) and reintroduction of its use (or increase of the level of activation / exposure), impact on the serious adverse event (when clinically feasible).
- other possible causes (e.g. an underlying or concurrent illness / clinical condition or / and an effect of another device, drug or treatment) have been adequately ruled out.
- harm to the subject is due to error in use.
- the event depends on a false result given by the investigational device used for diagnosis, when applicable.

In order to establish the relatedness, not all the criteria listed above might be met at the same time, depending on the type of device / procedures and the serious adverse event.

For each AE a severity description should be given.

Severity	Description
Mild	The event is easily tolerated and does not limit everyday activities; the subject may experience slight discomfort.
Moderate	The event is sufficiently discomforting to interfere with everyday activities.
Severe	The event prevents normal everyday activities; the subject may experience intolerable discomfort or pain.

Expectedness for each AE will be determined based on the information in sections 3.4 and 4 of the Investigator's Brochure.

Coding of AEs and medical history will be done using Medical Dictionary for Regulatory Activities (MedDRA) 25.1, or the most recent version if this has changed. If there is an update to MedDRA during the course of the investigation the most recent version will be used by the CRO.

Concomitant medications are coded by the CRO using the WHO dictionary (including ATC coding).

8.3 Reporting of Adverse Events

In the event of an SAE, SADE, USADE or device deficiency that could have led to an SAE, the Investigator must report the event using the appropriate form to the Sponsor's Adverse Event Management Team (AEMT) by email: [REDACTED] including in the email vendor and Sponsor Study Managers within 24 hours of knowledge of the event.

The out of hours emergency phone number is [REDACTED] if consultation is required by the Investigator.

This emergency phone number will be confirmed to the Investigator at the Investigation Initiation Visit.

All SAE / SADE / USADE forms must be provided via email including reports of device deficiency that could have led to a SAE/ SADE/ USADE. Any inconsistencies in the information received from the Investigator will be clarified on an updated SAE / SADE form. The Investigator must retain a copy of all the forms in the Investigator Site File.

The Investigator, if required by regulations, must inform their local Independent Ethics Committee (IEC) / Research Ethics Committee (REC) / Institutional Review Board (IRB) of all SAE / SADE / USADEs and reportable Device Deficiencies occurring in the investigation as per Sponsor instructions as described in the Safety Management Plan.

SAE / SADE / USADEs, Device Deficiencies will be reported to the appropriate regulatory authorities by the Sponsor in accordance with the authorities' requirements. The Sponsor is responsible for expedited reporting of all SAE / SADE / USADEs and reportable Device Deficiencies to relevant authorities. The Investigator is responsible for expedited reporting of all SAE / SADE / USADEs and reportable device deficiencies to the IECs / IRBs as required by regulations. If the event requires expedited reporting, the AEMT and Investigator will take actions as per the investigation specific Safety Management Plan.

The Investigator must report all reportable events to the sponsor immediately but not later than 24 hours after investigational site investigation personnel's awareness of the event.

8.4 Follow-up of Adverse Events

All SAE / SADE / USADEs and all AE / ADEs that have not resolved by the end of the investigation will be followed up by the Investigator until resolution or until the Investigator believes there will be no further change, whichever is the earlier. This may involve the subject making additional visits to the site.

In the case of loss to follow-up, at least two documented attempts to contact the subject must be made by the Investigator or designee before this is defined.

The end of the investigation is defined as the last visit of the last subject in the investigation.

All SAE/SADE/USADEs and all AE/ADE that cause premature withdrawal of the subject from the investigation and have not resolved by the end of the clinical investigation will be followed up by the Investigator until resolution or until the Investigator believes there will be no further change.

This may involve the subject making additional visits to the site. The minimum data required are the subject number, suspected investigational product, final outcome and date, which may be obtained by the Investigator in a documented telephone conversation with the subject or subject's general practitioner (GP) / Primary Care Physician (PCP).

Subjects who experience the onset of an (S)AE after the last visit (end of the investigation) will not need to be recorded.

8.5 Misuse and Medical Device administration Errors

The Sponsor defines "misuse" as situations where the medical device is intentionally and inappropriately used not in accordance with the authorised product information.

All incidences of misuse are reportable to the Sponsor irrespective of the presence of an associated AE. The misuse and any associated untoward event will be captured on an AE / ADE eCRF page or on a SAE / SADE / USADE form.

Medical device administration errors are any unintentional errors in administration which relates to:

- Using / being administered an incorrect medical device
- Using / being administered the medical device by the wrong route of administration / application
- The accidental administration of the medical device to a person who is not a subject within the investigation

Medical device administration errors are reportable to the Sponsor irrespective of the presence of an associated AE. Medical device administration errors with or without an associated untoward event will be captured on an AE / ADE eCRF page or on a SAE / SADE / USADE form.

8.6 Pregnancy

Pregnancy in a female subject is considered a collectable event and will be recorded as an AE in all cases. It will be qualified as an SAE only if it fulfils SAE criteria.

Pregnant subjects must immediately be withdrawn from the clinical investigation and the Sponsor must be promptly notified of the event. Any pregnancy during the investigation will be reported to the Sponsor within 24 hours of becoming aware of the pregnancy. The course and outcome of the pregnancy should be followed up carefully by the Sponsor Pharmacovigilance personnel (Drug Safety Officer) as part of their safety monitoring responsibilities and will not form part of the investigation dataset. Any abnormal outcome regarding the mother or the child should be documented and reported.

9 STATISTICAL CONSIDERATIONS

All statistical analysis will be conducted by the Vendor. The statistical software that will be used for the analysis will be SAS® version 9.4 or newer. All data will be listed by treatment group.

In general, continuous data will be summarised by treatment group using the following descriptive statistics: n, mean, standard deviation, median, minimum and maximum. Categorical data will be summarised by treatment group as the number and percentage of subjects in each category.

9.1 Statistical Analysis Plan

Details of statistical methods and analysis will be documented in the Statistical Analysis Plan (SAP) which will be finalised before the first subject is screened.

If there are any deviations to the proposed statistical analysis as described in this protocol these will either be documented in a protocol amendment and/or the final SAP prior to First Subject First Visit with the rationale and impact of the changes addressed.

9.2 Interim Analysis

No interim analysis will be performed.

9.3 Analysis Datasets

The Full Analysis Set (FAS) will include all randomised subjects who enter the Treatment Phase of the study. The FAS will be used to assess the primary endpoint and all other endpoints that are assessed during the Treatment Phase, with the exception of adverse events. Subjects will be assigned to treatment to which they were randomised.

For the FSFI (total score and percentage of subjects achieving at least a 4-point change in total score), an analysis will also be performed on the Per Protocol (PP) population. The PP population will exclude subjects who have not been compliant with the requirements of at least one coital act per week during both the run-in and 4-week IP use period of the Treatment Phase, as well as using IP at least once per week for penile/vaginal intercourse during the treatment period. In addition, subjects who use less than 80% of their assigned product (<9.6g) will be removed from the PP population. Subjects may be excluded from the PP population due to other reasons that may impact the evaluation of study products and these will be identified prior to database lock. Subjects will be assigned to treatment received.

The Safety Population will include all randomised subjects and will include subjects who take part in the Tolerance Phase and/or the Treatment Phase. The Safety Population will be used for producing demographic, adverse event and other safety tables. Subjects will be assigned to treatment received.

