Subjects:	
In this synopsis, female participant is referred to as the subject. Information on the activities undertaken by the male partner is specifically noted.
 
The investigation population will include an approximate 1:1 ratio of pre-menopausal to post-menopausal, with a difference of up to 40:60 (up to a maximum of 60% in either sub-population) being allowed. 33 subjects will be randomised to each treatment group. A subset of 22 subjects will be selected in a 1:1 treatment allocation ratio to participate in the Tolerance Phase of the investigation.
 
Summary of Inclusion and Exclusion Criteria:
 
Only subjects to whom all the following conditions apply will be included:
 
Universal Inclusion Criteria:
 
 1. Subject and their male partner have provided written informed consent. 2. Subject is female and both subject and their male partner are aged at least 18 years. Maximum age of female subject is 65 years. 3. Female subject and their male partner in a mutually monogamous heterosexual relationship (≥ 3 months) who are sexually active, defined as having sexual intercourse at least once a week. (Note: The number of sexual intercourses may comprise twice in one week to account for a menstrual period break.) 4. Female subject that agrees to have a gynaecological pelvic examination to ensure no significant disease findings and have intact skin and mucous in the test region (vaginal and vulvar / intimate area) except skin dryness as visually assessed by the gynaecologist at all the relevant time points. 5. Female subject that agrees to an oral exam by a dermatologist to ensure no significant disease findings and have intact skin and mucous in the test region (oral cavity - including lips, inside lining of the lips, cheeks (buccal mucosa), teeth, gums, tongue, the floor of the mouth, roof of the mouth (hard palate) and area behind wisdom teeth (retromolar trigone)). 6. Subjects reporting mild to moderate vaginal dryness and dyspareunia during sex (when not using lubricant) in the past 3 months as confirmed by a score of 1 or 2 for vaginal dryness and 1 or 2 for dyspareunia on the Verbal Rating Scale (VRS) of dyspareunia and vaginal dryness.
------------------	--

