1.3 Treatment Rationale

The proposed clinical investigation is a parallel-design investigation to determine the effectiveness and safety of one water-based personal lubricant and one silicone-based personal lubricant for the relief of intimate discomfort associated with vaginal dryness. [REDACTED]

The clinical investigation will include two phases: the Tolerance Phase, followed by the Treatment Phase (use-as-intended phase).

During the Tolerance Phase, a pea-sized amount of IP and comparator will be used for oral assessment and a 3 g of IP will be used for gynaecological assessments. The effects of the IPs on vulvovaginal and oral mucosal tissues, [REDACTED] will be assessed to verify the safety of the IPs for their intended purpose. This phase will be carried out in the clinical setting to allow objective assessments by the investigator (gynaecologist and dermatologist), although the subjects will be asked to complete questions relating to their perception of the tolerability of [REDACTED] on vulvovaginal and oral mucosal tissues.

Use of a comparator was deemed necessary for the oral mucosal assessment to further assess the difference, if any, in the subjects' perception of the test lubricants with sensory effects, as compared to the comparator without the sensory effect. The investigator (dermatologist) carrying out the oral mucosal assessment will also note any differences during the assessment.

The use-as-intended phase will be mainly based at home, with subjects using the lubricant during each sex occasion and recording the use of the product in their diaries. Subjects will engage in vaginal penetrative sex at least once per week (or twice per week to account for a menstrual period break) over a 4-week period but will not be prohibited from engaging in other forms of sexual activity (e.g. receptive oral/anal sex, non-penetrative and penetrative masturbation with a sex toy, partner's fingers or solo). Subjects will not be prohibited from using condoms, but this will not be the only form of contraception and the use will be captured in the diary. This will ensure that the subjects are not changing their routine to the extent that the participation in the clinical investigation is significantly interfering with their normal life and that the conditions of the clinical study are as close to real life as possible.

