6.4.2 Treatment Phase

Subjects will engage in vaginal penetrative sex at least once per week but will not be prohibited from engaging in other forms of sexual activity (e.g. receptive oral/anal sex, non-penetrative and penetrative masturbation with a sex toy, partner's fingers or solo). Subjects will not be prohibited from using condoms, but this will not be the only form of contraception and the use will be captured

in the diary. At product dispensing, subjects will be provided with a demonstration of a 3 g amount of lubricant for reference. The subjects will be asked to apply their allocated IP to the vagina and intimate area in approximately 3 g increments. The number of re-applications required during sexual intercourse will be recorded in the diary. Subjects can apply the IP up to 4 times per day where 3 g is considered to be a single application. Subjects will be expected to use their applied IP at least once a week over a 4-week period. The number of penetrative penile/vaginal sexual intercourses may comprise twice in one week to account for a menstrual period break.

Regular lubricant users will be instructed to use the lubricant as they would normally i.e. for vaginal, anal and / or oral sexual intercourse, ensuring that the IP is used at least once a week for vaginal penetrative sexual intercourse. Those subjects who do not usually engage in anal or oral will be instructed to use the product for vaginal sex only, for safety purposes. Only the lubricant (IP) dispensed by the clinical site is permitted for use during the investigation. Subjects will be instructed to not use any other vaginal products, remedy, vaginal moisturiser. The weight of the IP will be recorded when dispensed and again when subjects return to the clinical site following the 4-week use period.

Subjects that use the IP less than once a week during penetrative penile/vaginal sexual intercourse and/or do not follow the study restrictions e.g. use of other vaginal product other than the dispensed IP are forms of non-compliance, in which case subjects will be reminded of the need to remain compliant and what this may mean to their participation in the investigation.

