7.4 Treatment Phase

7.4.1 Run-In Phase

Following the confirmation of subject's eligibility, subjects entering the Treatment Phase will undergo a 4-week run-in phase. Those subjects that have completed the Tolerance Phase of the investigation, will move into the 4-week run-in phase of the Treatment Phase. During this run-in phase, subjects will be asked to refrain from using any personal lubricants or remedies for vaginal dryness during sexual activity. Subjects will be asked to consent to engaging in vaginal penetrative sex at least once per week during this 4-week period. The number of sexual intercourses may comprise twice in one week to account for a menstrual period break. Subjects will be asked to record into their diary the number and frequency of coital acts during this period, including when subjects were unable to have sexual intercourse without the use of a lubricant and/or for menstrual bleeding (pre-menopausal women).

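### The per-protocol rule in 9.3 does not carry over the menstrual-break allowance; read literally, it can drop pre-menopausal women who followed the conduct rules

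*Combined protocol and SAP*

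**What the plan says.** Section 9.3 defines the PP set by exclusion. A woman is removed if she did not comply with having "at least one coital act per week during both the run-in and 4-week IP use period of the Treatment Phase". A second weekly condition, on the product itself, is joined to the first: "as well as using IP at least once per week for penile/vaginal intercourse during the treatment period". A separate amount rule follows: "subjects who use less than 80% of their assigned product (<9.6g) will be removed from the PP population". Further exclusions may be identified before database lock. The PP set repeats the primary analysis of total FSFI and the 4-point response (9.3, 9.5.1.2).

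The conduct rules for the same two periods contain an allowance that 9.3 lacks:

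- Product-use period, section 1.3: intercourse "at least once per week (or twice per week to account for a menstrual period break) over a 4-week period".
- Product-use period, section 6.4.2: "The number of penetrative penile/vaginal sexual intercourses may comprise twice in one week to account for a menstrual period break".
- Run-in, section 7.4.1: "The number of sexual intercourses may comprise twice in one week to account for a menstrual period break".

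Inclusion criterion 3 (synopsis and 4.2.1) has the same note, but there it defines who counts as sexually active at entry. Section 6.4.2 also lists as non-compliant "Subjects that use the IP less than once a week during penetrative penile/vaginal sexual intercourse", without repeating the allowance given earlier in that section.

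**The concern.** A PP set is meant to keep the women who did what the protocol asked. Here the conduct rules accept a week without intercourse for menstruation if another week holds two acts, while the analysis rule asks for an act, and a product use, every week. Someone programming PP flags from 9.3 alone would code a check for each week and remove such a woman. Someone starting from 6.4.2 and 7.4.1 would keep her. Both could defend their choice, and a pre-specified population should not leave that open.

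The loss can occur only among pre-menopausal women, and menopausal status is the randomisation stratum. A difference between PP and FAS results could then partly reflect a changed stratum mix rather than compliance. The planned FSFI summaries by menopausal status use the FAS only (9.5.1.2), so they would not show it.

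**Working it through.** **Step 1: reproduce the plan's figure.** One application is about 3 g (1.3, 6.4.2), and use is expected at least once a week for 4 weeks. That gives 4 × 3 g = 12 g, and 0.80 × 12 g = 9.6 g, which matches 9.3. So the amount rule looks at the total over four weeks, not at each week.

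**Step 2: apply the rules to a woman who uses the allowance.** Read literally, 9.3 sets 4 + 4 weekly checks for a coital act and 4 weekly checks for product use. Take weekly counts made up of 0, 1, 1 and 2 in the product-use period, for example 2+0+1+1. There are 4!/2! = 12 orderings. Each has 4 acts and, at one application per act, 4 × 3 g = 12 g.

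| Rule | Orderings passing |
|---|---|
| At least 9.6 g used | 12 of 12 |
| At least one act or use in every week (9.3 read literally) | 0 of 12 |
| Weekly rule with the allowance | 12 of 12 |

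Only the weekly wording removes her. The same pattern in the run-in also fails the literal rule; no amount rule applies there. Grams do not count acts, because 6.4.2 permits re-application; the 12 g figure assumes one application per act.

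**Step 3: how far the PP mix could move.** Section 4.1 gives 30 completers per arm and a split of up to 40:60. Applied to completers, that is 0.40 × 30 = 12 to 0.60 × 30 = 18 pre-menopausal women. The documents give no rate of menstrual weeks without intercourse, so the number removed, k, is an assumption. With P pre-menopausal completers:

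- pre-menopausal share after removal = (P − k)/(30 − k);
- shift in the PP mean for each 1-point difference in mean FSFI change between strata = P/30 − (P − k)/(30 − k).

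| P of 30 | k = 1 | k = 3 | k = 6 |
|---|---|---|---|
| 12 (40%) | 11/29 = 37.9%; 0.021 | 9/27 = 33.3%; 0.067 | 6/24 = 25.0%; 0.150 |
| 15 (50%) | 14/29 = 48.3%; 0.017 | 12/27 = 44.4%; 0.056 | 9/24 = 37.5%; 0.125 |
| 18 (60%) | 17/29 = 58.6%; 0.014 | 15/27 = 55.6%; 0.044 | 12/24 = 50.0%; 0.100 |

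The shifts assume that removed women have the mean change of their stratum and that nobody else leaves the PP set. The documents give no difference between strata.

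**The case against.** The best reply is that 9.3 speaks of complying with requirements, and the requirements are set in 6.4.2 and 7.4.1, where the weekly frequency and the menstrual note stand together. On that reading the 2+0+1+1 woman is compliant and stays in. The short form without the note is also common in the protocol: the synopsis (treatment regimen and methodology), 3.1 and 7.4.2 all use it. This has force. A reader might infer that the rule certainly excludes compliant women, and the documents do not support that. But 9.3 goes on to spell out the requirement without the note and without a cross-reference, and unlike the other short forms it decides whose data are analysed. Its clause on other reasons can only add exclusions, so it cannot bring a woman back.

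Three further points stand. The eligibility note is one criterion printed twice, so the conflict rests on the three on-study statements. The non-compliance sentence in 6.4.2 leads only to a reminder and excludes nobody. The separate SAP announced in 9.1 is not in the material reviewed; if it already applies the allowance to PP, only a cross-reference in 9.3 is missing.

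The planned subject-level listings and sexual-activity summaries (9.6) would help a careful reader notice a changed mix, but no PP summary by stratum is planned.

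**Conclusion.** The point holds as a minor inconsistency between the PP definition and the conduct rules. It leaves PP membership undetermined for pre-menopausal women who used the allowance; read literally, 9.3 removes them. It does not reach all pre-menopausal women, only those who missed a whole week for menstruation and made it up in another.

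The number affected is unknown. The bounds, from none to all 12–18 pre-menopausal completers per arm, say little. In the illustrations the PP mean moves by 0.01 to 0.15 points for each 1-point difference between strata, so the effect is likely small unless many women are affected.

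A reader might infer that the trial's main conclusion is biased or loses power. The documents do not support that: the primary endpoint is assessed on the FAS, PP is a supportive repeat, and the success criterion does not depend on it. Even for PP, this cause alone would have to remove six women per arm to bring 30 down to the 24 completers given in 3.3 for 90% power on the primary endpoint.

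**What to change.** In 9.3, or in the SAP before first screening, state that both weekly PP conditions (coital act and product use) are assessed with the menstrual-break allowance of 6.4.2 and 7.4.1, so that a woman who used it is not excluded from PP for that reason. Reconcile the non-compliance sentence in 6.4.2 with the allowance in the same section. The sponsor should also set how diary weeks and menstrual breaks are counted, using the diaries and the menstrual dates recorded at Treatment Phase Visits 2 and 3; 9.3 does not say how a week is delimited.

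The cost is one sentence, one reconciling clause and a short counting rule, with no new procedure. There is a small downside in the product-use period. The run-in diary is said to record menstrual bleeding (7.4.1), but the product-use diary is not, although its list in 6.12.2 is open-ended, and Visit 3 records only the last period. Some breaks may therefore need a diary comment or a data query to confirm.
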